5.5. Exposure to Investigational Product

The following parameters will be summarized using the Safety Set and listed:

- Total dose administered (mg)
- Duration of treatment with pegcetacoplan (days) defined as (last infusion date – first infusion date + 1)
- Number and percentage of subjects who received at least one infusion
- Number and percentage of subjects with any infusions missed
- Number and percentage of subjects with one or more incomplete infusions
- Number and percentage of subjects with any infusions interrupted

5.6. Measurements of Treatment Compliance

Percent compliance will be summarized using the Safety Set and listed. Compliance is calculated as follows: Compliance (%) = total number of study infusions taken / total number of expected infusions, multiplied by 100.

The number and percentage of subjects who had a percentage of drug compliance range by increment of 10% (<80%, ≥ 80% - < 90%, ≥ 90 - ≤100%, and >100%) will also be summarized.

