## 9.4. Exit Visit

All subjects will return to the clinic facility for the exit visit, 8 weeks following the final dose of pegcetacoplan, on Day 420 (or sooner if the subject discontinues prior to Week 52).

Study participation for each subject will be concluded following completion of the exit visit. If a subject withdraws from the study prior to the scheduled exit visit, all exit visit assessments should be performed at the subject's final visit to the clinic, including collection of blood samples for PK and/or PD assessments, as well as a postdose antigenicity sample, if not yet collected.

The exit visit procedures are listed in the Schedule of Activities (Table 1):

- Arrange courier service to pick up 24-hour urine collection to deliver to site
- Procure 3 previously collected consecutive uPCR samples to site
- Blood samples for laboratory assessments (see Schedule of Activities [Table 1] for details)
- Concomitant medications
- AE review
- Anti-pegcetacoplan/anti-PEG circulating antibodies assay
- eGFR assessment
- Urinalysis (see Schedule of Activities [Table 1] for details)
- Vital signs
- 12-lead ECG
- PK sample

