13.6. Handling of Missing, Unused, and Spurious Data

13.6.1. Missing Date of Investigational Product

When the date of the last dose of investigational product is missing for a subject in the Safety Set, all efforts should be made to obtain the date from the investigator. If it is still missing after all efforts, then the last visit date will be used in the calculation of treatment duration.

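### SAP 13.6.1 replaces a missing last-dose date with the last visit date, which for a subject in follow-up counts about 56 off-drug days as treatment

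*SAP*

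**What the plan says.** SAP 5.5 summarises exposure in the Safety Set and includes "Duration of treatment with pegcetacoplan (days) defined as (last infusion date – first infusion date + 1". The end point of that formula is an infusion, not a visit.

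SAP 13.6.1 covers a missing last-dose date. First, "all efforts should be made to obtain the date from the investigator". Then: "If it is still missing after all efforts, then the last visit date will be used in the calculation of treatment duration". Nothing restricts the substitute to a visit at which the subject was still on drug. SAP 13.6.2.2 makes the same substitution when it imputes incomplete medication stop dates, and SAP 13.6.3 carries those rules over to AE stop dates.

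The protocol puts the last Part A visit well after dosing for anyone not entering Part B. Protocol 9.4 places the exit visit "8 weeks following the final dose of pegcetacoplan, on Day 420". Under Protocol 9.3, subjects who stop early and leave the study have a visit 2 weeks after stopping and an exit visit 6 weeks later.

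On compliance, SAP 5.6 has "Compliance (%) = total number of study infusions taken / total number of expected infusions, multiplied by 100". SAP 5.5 separately reports "Total dose administered (mg") and "Number and percentage of subjects with one or more incomplete infusions".

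**The concern.** The substitute date measures how long a subject was observed, while the quantity being summarised is how long the subject was treated. The two are close for a subject still dosing at the last visit. They differ by the whole follow-up period for a subject who has stopped. For a subject who attends follow-up, the error always runs toward more treatment than was given.

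The groups are small (up to 9 and up to 3 subjects), so one affected record is visible in a group mean. What is at stake is the accuracy of a descriptive exposure table, not an efficacy result.

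**Working it through.** **Inputs**
- Duration = last infusion − first infusion + 1 (SAP 5.5).
- Completer's final dose Day 364 and exit visit Day 420, window ±7 days (Protocol 9.4 and Table 1; same target days in SAP 13.4).
- Early discontinuer leaving Part A: 2 weeks plus 6 weeks (Protocol 9.3).
- Group 2 first dose at Visit 7 or 8, after the Week 12 biopsy (Protocol 9.2.3). Taken here as Day 84 to Day 105, the latter being Day 98 plus the 7-day window.
- Part B early discontinuer: termination visit up to 6 weeks after stopping, exit visit 6 weeks later (Protocol 15.1.2).

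**Step 1: the plan's own gap.** 420 − 364 = 56 days, which reproduces the protocol's 8 weeks. For an early discontinuer, 14 + 42 = 56 days. The 56 days is nominal: the exit window gives 413 − 364 = 49 to 427 − 364 = 63 days. If the last infusion falls on Day 4 of Week 52 (Day 361), the gap is 420 − 361 = 59 days.

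**Step 2: duration with the true and the substituted date**

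| Subject | True duration (days) | With last visit (days) | Excess |
|---|---|---|---|
| Group 1 completer, Day 1 to 364 | 364 | 420 | 56/364 = 15.4% |
| Group 2 completer, start Day 84 | 281 | 337 | 56/281 = 19.9% |
| Group 2 completer, start Day 98 | 267 | 323 | 56/267 = 21.0% |
| Group 2 completer, start Day 105 | 260 | 316 | 56/260 = 21.5% |
| Group 1, stops Day 84, exits Day 140 | 84 | 140 | 56/84 = 66.7% |
| Enters Part B; last dose Day 361, last Part A visit Day 364 | 361 | 364 | 3/361 = 0.8% |

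The last row shows where the rule is nearly harmless. A Part B early discontinuer is not: the exit visit can fall 42 + 42 = 84 days after stopping.

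**Step 3: effect on a group mean.** One affected subject moves a 3-subject Group 2 mean by 56/3 = 18.7 days and a 9-subject Group 1 mean by 56/9 = 6.2 days.

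**Step 4: does it reach the TEAE window?** SAP 7.1 closes that window 56 days after the last dose. SAP 13.6.1 names only treatment duration, so the substitute does not feed the window as written. Even if it were programmed that way, AE collection stops at the exit or early termination visit (Protocol 11.2). A Part A completer's correct window closes on Day 364 + 56 = 420, and the exit visit is in window until Day 427, so at most about 7 days could be added.

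**Step 5: compliance.** At two infusions a week, 52 weeks gives 104 expected. The documents give no rate of incomplete infusions, so the following counts are assumptions.
- 10 half-delivered infusions: by dose, (104 − 5)/104 = 95.2%. By count it is 100% if they count as taken, or 94/104 = 90.4% if they do not. The direction of any discrepancy depends on the missing definition.
- 20 half-delivered: by dose, (104 − 10)/104 = 90.4%, which stays in the SAP's 90-100% band.
- Over 12 weeks (24 expected), 5 half-delivered: by dose, (24 − 2.5)/24 = 89.6%, one band lower than 100%.

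**The case against.** The strongest reply is that the date rule is a last resort. It applies only after the investigator has been asked, and the protocol creates several records that should supply the date: dosing diaries (8.2), a log for every infusion (8.4.4), returned packaging and accountability (8.7), and a recorded treatment discontinuation date (7.2.2). No analysis set, threshold or efficacy analysis uses duration or compliance. The primary endpoint is read at Week 12 and counts premature treatment withdrawal as non-reduction. Exposure can also be judged from measured drug concentrations. All of this stands, and it makes the point minor. It does not make the rule right when it is invoked: none of these safeguards stops the substitute from being an off-drug visit.

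A reader might draw three stronger conclusions, which the documents do not support.
- **That SAP 5.6 counts a part-delivered infusion as a full one and so overstates compliance.** The SAP never says so; it leaves *taken* undefined. Total mg and incomplete infusions are reported separately in SAP 5.5, so delivered dose is not hidden.
- **That the 56-day TEAE window would run from the substituted date.** SAP 13.6.1 is limited to duration, SAP 13.6.2.2 concerns stop dates, and AE collection ends at the exit visit.
- **That these rules affect how a lack of C3c reduction is interpreted.** The plan makes no such use of either figure.

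**Conclusion.** The point holds as a minor flaw in SAP 13.6.1. When the rule is triggered for a subject outside Part B who attended follow-up, treatment duration is overstated by nominally 56 days: about 15% for a Group 1 completer, about 20-22% for a Group 2 completer, and proportionally more for an early discontinuer.

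This assumes that the exit visit took place on schedule, that dosing ran to Day 364 for completers, and that the date could not be recovered by query. That combination should be rare. The consequence is confined to the descriptive exposure summary, with a parallel effect on imputed stop dates through SAP 13.6.2.2. The C3c analysis is unchanged, and so is the TEAE window as written. The treatment of incomplete infusions in SAP 5.6 is a gap in definition worth closing, not an error.

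**What to change.** In SAP 13.6.1, replace the last-visit rule with an ordered one:
1. Use the last infusion documented in the dosing diary, infusion log or accountability record.
2. Failing that, use the earliest of the last visit date, the recorded treatment discontinuation date and the end of the treatment period (the Week 52 visit for a subject not entering Part B).
3. Flag the date as imputed in the listing.

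Apply the same substitution in SAP 13.6.2.2 so that the two sections agree.

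A cap is preferable to falling back on the last on-treatment visit. Visits are 6 weeks apart between Weeks 24 and 48 and 12 weeks apart in Part B, so that fallback could understate duration by nearly a whole visit gap.

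The cost is a few lines of SAP text using records the protocol already requires. The imputed duration will be somewhat shorter and still approximate: an early discontinuer with no recorded discontinuation date would still be assigned the last visit.

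Optionally, state in SAP 5.6 whether an incomplete infusion counts as taken, or show mg delivered over mg planned beside the count-based figure.

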5.7. Protocol Deviations

All protocol deviations will be reviewed and documented before database lock. Protocol deviations are being captured in accordance with the protocol deviation management plan. They may also be identified through programmable checks of the data.

The CRO/Apellis will classify major and minor protocol deviations per the agreed protocol deviation management plan. The Apellis study team will review the protocol deviations and their classification throughout the study and before database lock.

The number and percentage of subjects with protocol deviations will be summarized by importance of deviation for ITT Set and listed.

6. EFFICACY ANALYSIS

6.1. Analyses of Primary Efficacy Endpoint

The primary efficacy endpoint is the proportion of subjects with reduction in C3c staining on renal biopsy at Week 12.

The baseline renal allograft biopsy will be taken as defined per Protocol Section 9.1.3.

The proportion of subjects with reduction in C3c staining at Week 12 will be tabulated, along with the 95% confidence intervals (CIs).

Categories for C3c staining are: 0 (including negative and trace), 1, 2, 3, and NA (meaning no C3c staining available or no glomeruli in the sample stained for C3c). Reduction in C3c staining is defined as decrease of at least 2 orders of magnitude of intensity from baseline (e.g., baseline result being 3 and Week 12 result being 1 or 0). Missing or NA results at Week 12 will be listed separately. A composite strategy will be used for addressing intercurrent events. The C3c staining status at or after the initiation of any of intercurrent events, including but not limited to, the use of prohibited concomitant medication, starting renal replacement therapy due to worsening of underlying disease, use of rescue therapies, premature withdrawal from the treatment, will be regarded as non-reduction. The initiation of intercurrent events will be reviewed by medical team and provided to biostatistics team.

Sensitivity analysis such as using treatment policy strategy for handling intercurrent events, meaning that Week 12 C3c staining status will be collected and analyzed regardless of an intercurrent event has occurred or not, will also be performed. Supportive analysis may be conducted based on those who have both baseline and Week 12 C3c staining results.

6.2. Analyses of Secondary Efficacy Endpoints

The proportion of subjects with reduction in C3c staining on renal biopsy at Week 52, change from baseline biopsy in C3c staining over time, the proportion of subjects with stabilization or improvement in eGFR or serum creatinine concentration over time, change and percentage change from baseline in eGFR and serum creatinine concentration over time, are the secondary efficacy endpoints.

The proportion of subjects with reduction in C3c staining on renal biopsy at Week 52 will be tabulated. The strategies to handle intercurrent events are same as for the primary endpoint by using composite strategy and treatment policy strategy. Changes from baseline biopsy in C3c staining over time will be summarized. A spaghetti plot of C3c staining throughout the study will be provided.

The proportion of subjects with stabilization or improvement in eGFR (defined as no more than a 25% decrease relative to baseline) over time will be tabulated. The Chronic Kidney Disease–Epidemiology Collaboration (CKD-EPI) creatinine equation for adults will be used to calculate eGFR. Changes and percentage changes from baseline in eGFR will be summarized over time.

The proportion of subjects with stabilization or improvement in serum creatinine concentration (defined as no increase or an increase of no more than 25% from baseline) over time will be tabulated. Changes and percentage changes from baseline in serum creatinine concentration will be summarized over time.

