#### 7.2.2. Reasons for Discontinuation

The date of and reason for treatment discontinuation must be determined by the investigator and recorded in the subject's medical record. If it is determined that there was more than one reason for the discontinuation, each reason should be documented in the source document, and the most clinically relevant reason, as determined by the investigator, should be identified. Treatment may be discontinued and/or a subject's participation in the study may be discontinued for any of the following reasons:

- Any serious adverse event (SAE), clinically significant AE, severe laboratory
  abnormality, intercurrent illness, other medical condition (including infections),
  or circumstance that indicates to the investigator that continued participation is not in
  the best interest of the subject
- Subject withdrawal of consent: At any time, a subject's participation in the study may
  be terminated at his/her request or on the basis of the investigator's clinical judgment.
  The reason for subject withdrawal will be noted in the subject's source document.
- Subject fails to adhere to the protocol requirements (eg, drug noncompliance, failure to return for defined number of visits)
- Subject is lost to follow-up: the subject stopped coming for visits, and study
  personnel were unable to contact the subject
- Termination of the study by the sponsor or regulatory authorities
- Liver toxicity (refer to Section 7.2.3 for further details)
- Pregnancy, as indicated in Section 11.3
- Failure to meet randomization criteria

Any subject who discontinues treatment early or is withdrawn from the study early due to a treatment-emergent adverse event (TEAE), whether serious or nonserious, will be followed until the TEAE resolves (returns to normal or baseline values) or stabilizes or until it is judged by the investigator to no longer be clinically significant.

If consent is withdrawn, no further study evaluations are to be performed and no attempts are to be made to collect additional data.

Additionally, the sponsor may stop the study at any time for safety, regulatory, legal, or other reasons aligned with good clinical practice (GCP). This study may be terminated at the discretion of the sponsor or any regulatory agency. An investigator may elect to discontinue or stop the study at his/her study site for any reason, including safety or low enrollment.

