# 12.3.2. Analysis of Secondary Efficacy Endpoints

Changes from baseline biopsy in C3c staining over time will be summarized by treatment group. The proportion of subjects with reduction in C3c staining on renal biopsy after 52 weeks of treatment will be tabulated.

Changes and percentage changes in eGFR and serum creatinine concentration over time will be summarized by treatment group. eGFR and serum creatinine concentration will be measured at baseline and at each postrandomization assessment. The proportion of subjects with stabilization or improvement in each parameter will be tabulated. The Chronic Kidney Disease–Epidemiology Collaboration (CKD-EPI) creatinine equation for adults will be used to calculate eGFR, and a stable or improved eGFR will be defined as no more than a 25% decrease in eGFR relative to baseline. A stable or improved serum creatinine concentration will be defined as no increase or an increase of no more than 25% from baseline.

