4.2. Intent-to-Treat Set

The intent-to-treat (ITT) set consists of all subjects who are randomized.

The ITT set will be used for the summary of demographics, baseline characteristics, subject disposition, and analysis of all efficacy data.

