13. DATA HANDLING CONVENTIONS

13.1. General Data Reporting Conventions

All statistical analyses will be performed using SAS® (Version 9.4 or higher, SAS Institute Inc., Cary, NC, USA).

Categorical variables will be tabulated as number of subjects and percentage of total number of subjects in the given analysis set as noted for each category. Percentages will be reported to one decimal place. Descriptive statistics will be used to summarize continuous variables including number of subjects, mean, standard deviation (SD), median, Q1, Q3, minimum and maximum. Mean, Q1, Q3, and median will be reported to 1 more decimal place than the raw data, while the SD will be reported to 2 more decimal places than the raw data. Minimum and maximum will be reported the same as the original data.

Subject specific listings will be provided by treatment group, subject ID, Study Period and visit, if applicable.

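### The eGFR and creatinine responder endpoints have no rule for renal replacement therapy, so a creatinine value lowered by that therapy can be counted as stable kidney function

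*SAP*

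**What the plan says.** SAP 6.1 sets a composite strategy for the primary endpoint. It acts on one variable, "The C3c staining status at or after the initiation of any of intercurrent events", and has one outcome, non-reduction. The events it lists include "starting renal replacement therapy due to worsening of underlying disease, use of rescue therapies". SAP 6.2 refers back to this once: "The strategies to handle intercurrent events are same as for the primary endpoint by using composite strategy and treatment policy strategy". That sentence stands in the C3c paragraph, directly after the Week 52 C3c proportion.

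The eGFR and creatinine endpoints have their own paragraphs in SAP 6.2. The creatinine endpoint is the proportion with "stabilization or improvement in serum creatinine concentration (defined as no increase or an increase of no more than 25% from baseline) over time". The eGFR endpoint is the proportion whose eGFR has fallen by no more than 25%, with eGFR calculated by the CKD-EPI creatinine equation. Neither paragraph mentions intercurrent events. Protocol 12.3.2 gives the same thresholds, states "The proportion of subjects with stabilization or improvement in each parameter will be tabulated", and adds no rule. SAP 13.3 to 13.6 (baseline, visit windows, repeat assessments, missing data) contain nothing that recodes or excludes values after RRT. On the population, SAP 4.2 says "The ITT set will be used for the summary of demographics, baseline characteristics, subject disposition, and analysis of all efficacy data".

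**The concern.** RRT removes creatinine from the blood. Once it starts, serum creatinine and the eGFR calculated from it can reflect the therapy rather than the graft. The plan counts RRT for worsening disease as failure for the histological endpoint, yet is silent for the two endpoints that RRT distorts directly.

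A programmer who follows SAP 6.2 exactly could therefore report a subject on RRT as stable or improved. The graft-loss summary in SAP 7.1 could then report a lost graft for the same subject. In Group 1 the miscount would make pegcetacoplan look better. In Group 2 during Weeks 1-12 it would narrow the descriptive contrast between the groups.

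**Working it through.** The plan gives no power or precision figure for these endpoints, so there is none to reproduce. The check has four steps.

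**1. Does the text prevent the miscount?** The SAP 6.1 rule names C3c staining status and ends in non-reduction. SAP 6.2 repeats the strategy only for C3c. Even if its sentence were meant for every secondary endpoint, non-reduction has no meaning for eGFR or creatinine. No other section supplies an outcome.

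**2. Can a value measured after RRT exist?** Protocol 12.3.2 has both variables measured at every postrandomization assessment. Stopping is discretionary: under Protocol 7.2.2, "participation in the study may be discontinued for any of the following reasons", and the list names neither RRT nor graft loss, although its general medical clause could be used. A subject who stays on schedule therefore keeps supplying values. Subjects who stop treatment can supply values at follow-up visits (Protocol 6.2.4 and 7.2.1), and those who leave can do so at the early termination and exit visits (Protocol 9.5). These off-schedule values reach a main-period visit only if the windows in SAP 13.4, written for safety laboratory, vital sign and ECG data, are also used for efficacy. The SAP does not say whether they are.

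**3. When would that value be scored stable?** Let creatinine before RRT be k times baseline, and let RRT lower it by a fraction f. The subject is scored stable if k(1 - f) ≤ 1.25, that is, if f ≥ 1 - 1.25/k. The documents give neither k nor f, so k is assumed over a range:

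| k (assumed) | 1 - 1.25/k | Fall needed |
|---|---|---|
| 1.5 | 1 - 0.833 | 16.7% |
| 2 | 1 - 0.625 | 37.5% |
| 3 | 1 - 0.417 | 58.3% |
| 4 | 1 - 0.3125 | 68.8% |

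For example, k = 2 and f = 0.5 gives 1.00 times baseline (no increase), and k = 3 and f = 0.6 gives 1.20 (stable). But k = 3 and f = 0.5 gives 1.50, which is correctly scored as not stable. The eGFR endpoint moves the same way, with its limit at 0.75 times baseline. At the entry floor of 15 mL/min/1.73 m² (Protocol 7.1.1) that limit is 0.75 × 15 = 11.25.

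**4. What does one miscounted subject do?** The shift is 1/n: 1/9 = 11.1 points at the planned Group 1 size, 1/3 = 33.3 at the Group 2 size, and 1/12 = 8.3 overall. For instance, Group 1 would read 9/9 = 100% instead of 8/9 = 88.9%. The exact 95% intervals are 66.4-100% and 51.8-99.7%. SAP 6.2 plans no intervals for these proportions; they are given here only for scale.

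**The case against.** The strongest reply is that several conditions must all hold. A subject must start RRT in the study period, have a creatinine measured afterwards, and have that value at or below 1.25 times baseline (or eGFR at or above 0.75 times baseline). The documents give no rate for any of these. The 1/n shift applies to any reclassified subject and says nothing about likelihood. All of this stands, and it limits the point to what can happen.

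Four stronger inferences are tempting, but the documents do not support them.

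- *Every subject on RRT would be scored stable.* Step 3 shows that some would still exceed the threshold.
- *The risk is about one in two.* Protocol 4.2 reports graft loss from recurrence in up to 50% of patients, but gives no time frame. It cannot be turned into a 52-week rate.
- *A subject with no value is automatically a non-responder.* SAP 13.1 says "Categorical variables will be tabulated as number of subjects and percentage of total number of subjects in the given analysis set", but then qualifies this by category, and SAP Section 1 leaves table specifications to a separate document. The denominator is not settled. Nor can one say which later visits of a subject who stops early would lack a value, because Protocol 6.2.4 notes that some Visit 15 and 16 assessments may still be needed.
- *There can be at most 12 subjects.* Protocol 7.2.5 allows replacement until 12 complete Week 52, while the ITT set is everyone randomized. A larger n makes the shift smaller.

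The reply also notes that a case would be visible: graft loss is summarized (SAP 7.1), all laboratory values are listed (SAP 7.2), and data issues are reviewed before lock (Protocol 12.2.6). That is true, but a listing does not correct the count, and a rule chosen after seeing the one affected subject is not prespecified.

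**Conclusion.** The concern holds in conditional form. Following the stated 25% thresholds exactly can give a wrong responder count, which makes this more than a missing detail. It rests on the general fact that RRT lowers serum creatinine, and on a measured value after RRT starts that falls within the threshold.

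The shift is 1/n per affected subject. The figures in step 4 assume the planned group sizes with every subject in the denominator. How often it would happen cannot be estimated from the documents.

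The reach is limited to descriptive secondary proportions. The primary endpoint already has a rule, and no hypothesis test or planned effect estimate is involved. It should be corrected because the groups are small, the proportions are themselves the reported result, and the SAP already treats RRT for worsening disease as failure elsewhere.

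**What to change.** Add to SAP 6.2 that, for the eGFR and creatinine responder endpoints, a subject is scored not stable at visits while on RRT and at all visits at or after graft loss. The medical team supplies the event dates, as in SAP 6.1. Scoring RRT only while it continues lets a subject who comes off temporary RRT be judged again on measured values. This differs from SAP 6.1, where status from the start of the event onward counts as failure, so the text should say that the difference is intended.

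Keep the as-observed tabulation as the treatment-policy sensitivity analysis. Record the change in SAP Section 15, which now reads as not applicable, because Protocol 12.3.2 defines these endpoints on measured values alone. Settle the wording before the database lock for the analysis concerned (SAP 3.5).

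The cost is a short addition to SAP 6.2, one extra table and the Section 15 entry. Graft-loss dates and RRT from causes other than the underlying disease must be added to the medical team's event list. No new assessments are needed. The stabilization proportion may come out slightly less favourable.
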